#### **Study Summary**

Study Start: February 13, 2017 (1 week run-in period) Accrual Start: February 20, 2017 (NCT03050918) Primary Outcome: Readmission within 30 days

[figure not shown]
Primary Analysis: Intention to Treat

- Study length/accrual period: ~7 months
- Follow up: 45 days
- Sample size: 3556 (1778 per arm)
- Baseline event rate = 13.5%
- Target detectable difference of 3.5% (13.5% controls, 10% intervention)
- Power 90% (chi square)

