#### Data Collection

Every weekday morning, a report will be generated from the Vanderbilt electronic medical record identifying all patients discharged from the hospital the previous day. This list will be transmitted securely to the study team. The list will then be randomized and uploaded to the study database within Research Electronic Data Capture (REDCap). This will occur using code written in R linked with the application program interface (API) function of REDCap. (See *Appendix II* – Randomization and REDCap API Database Upload Code). The code will upload patients assigned to the 2 study arms into separate database locations. The Intervention Arm Database includes a work list queue for the Study Phone Call Nurse. In addition, she will document interventions delivered via a form (*Appendix III* - Intervention Data Capture Form) for each patient's phone call encounter that will save this data as new variables within the database.

The Study Phone Call Nurse will continue to complete an existing form within the electronic health record, the Phone Call Starform (*Appendix I*) to document care provided via the phone call. For patients reached, the Study Phone Call Nurse will use the semi-structured script provided by the Starform to assess the patient's understanding of their discharge plan, screen for discharge assistance needs, and inquire about new symptoms requiring patient referral.

The majority of our study data will be obtained via Vanderbilt University Medical Center's Research Derivative. These variables include: 1) VUMC based primary outcome (hospital readmission to VUMC) data, 2) secondary outcome measures (patient satisfaction scores, all cause ED visits within 30 days, identified the need for assistance with discharge plan implementation, and 30 day mortality), 3) Hospital readmission risk score calculated for each patient before discharge which is included as part of the medical record, and 4) prespecified subgroup identifiers (see Figure 1).

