### **ANALYSIS PLAN**

#### General Approach

The study analysis will have 3 phases. The primary analysis will examine our primary outcome, hospital readmission within 30 days, via an intention-to-treat analysis where comparisons will be made between the 2 study arms. We will then examine secondary outcomes of all cause ED visits to Vanderbilt or VHAN ED and mortality. Given VUMC's interest in understanding characteristics of patients not reached via telephone, we will explore differences among those called and reached, called and not reached, and the control arm. In these 3 phases we will examine outcome differences by treatment assignment, age, gender, race, highest educational attainment, health literacy, established primary care status, patient satisfaction level, Medicare readmission penalty diagnosis status, and readmission risk score calculated at discharge as part of routine care at VUMC. Lastly, we will use descriptive statistics to quantify the need for patient assistance with discharge plan implementation (appointment scheduling or reminders, questions about new medications, durable medical equipment acquisition, referral for new symptoms, etc.) among patients in the intervention arm who are called and reached.

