#### Statistical Analysis

In our univariate analysis, differences among these patient characteristic groups will be assessed using the continuity corrected chi-square test or Mann-Whitney test for continuous outcomes and the Kruskal-Wallis test for categorical outcomes. In our multivariate analysis, we will examine the relationship between treatment assignment and our secondary endpoints using logistic regression. The study is not powered for a time-to-event analysis; however, we will explore time-to-readmission using the Cox proportional hazard model to understand the timing of when readmissions occur. In order to provide VUMC Leadership with preliminary efficacy data, we will perform an interim analysis at 50% enrollment ( $\sim$ 3.5 months) followed by the final analysis at study completion months ( $\sim$ 7 months). See **Appendix V** for details. We have pre-specified an  $\alpha$ -level of significance of 0.05 with penalties for a mid-study interim analysis per the O'Brian-Fleming alpha spending function allowing for an  $\alpha$ -significance level of 0.005 for the interim analysis and 0.048 for the final analysis.

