**Table 1 - Power and Sample Size Scenarios** 

	Conse	rvative	Ambitious	
Control Group Readmission Rate†	13.52%	13.52%	13.52%	13.52%
Intervention Group Readmission Rate	9.60%	9.10%	10.20%	9.70%
Power	80%	90%	80%	90%
Detectable Difference	3.9%	4.4%	3.3%	3.8%
Projected Study Sample Size	1117	1117	1582	1582

\*2 group X^2 test of equal proportions (equal n's), 2-sided text, final analysis  $\alpha$  = 0.048

illustrate conservative and ambitious enrollment scenarios with estimates for 80% and 90% power. Considering we have 1 Phone Call Study Nurse and will miss enrollment days for paid time off or sick days, we opted for a more conservative power target and detectable differences of 80% and 3.9% respectively. This carries an associated enrollment of 1117 patent per arm (n = 2234, or 11 patients per day).

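### The primary 30-day readmission comparison appears to be planned unadjusted, although a readmission risk score fixed before randomisation is already being extracted and could add precision

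*Combined protocol and SAP*

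**What the plan says.** **Primary analysis.** General Approach says 30-day readmission will be examined "via an intention-to-treat analysis where comparisons will be made between the 2 study arms". It names no test and no covariate. The Study Summary gives "Power 90% (chi square"), and the footnote to Table 1 (Power and Sample Size Scenarios) gives a two-"group X^2 test of equal proportions" at alpha 0.048. Appendix V, item 4, shows the VUMC readmission rate as a 2x2 table. Study Timeline, item 5, makes the final analysis the same as the interim apart from added data.

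**Regression.** Statistical Analysis says "we will examine the relationship between treatment assignment and our secondary endpoints using logistic regression".

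**Risk score.** Data Collection lists, among the Research Derivative variables, a "Hospital readmission risk score calculated for each patient before discharge". Study Length and Timeline places randomisation on the morning after discharge. The score is a subgroup variable (Outcome Measures), one of the factors by which outcomes are examined (General Approach: "In these 3 phases we will examine outcome differences by treatment assignment, age, gender, race", a list that ends with the score), and a baseline item (Appendix V, item 3).

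**Test wording.** For patient characteristic groups, Statistical Analysis names the "continuity corrected chi-square test or Mann-Whitney test for continuous outcomes and the Kruskal-Wallis test for categorical outcomes".

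**The concern.** A score built to predict readmission, and fixed before allocation, is a natural covariate for a readmission endpoint. Adjusting for it removes outcome variation that has nothing to do with the call programme. The plan collects the score and uses it in three other places, but not in the one estimate that decides the trial. What is at stake is some power and a narrower confidence interval, available without enrolling anyone else. This has some value in a design that settles for 80% power because there is one nurse and enrolment days will be missed (Power Calculation).

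Two smaller matters sit in the same section. The primary test is not named, so it is unclear whether its chi-square is continuity corrected. And Kruskal-Wallis is assigned to categorical outcomes; for a nominal variable such as race, a rank test depends on an arbitrary coding.

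**Working it through.** **1. Is the primary comparison unadjusted?** No sentence says so. The inference rests on four things: sizing by a two-group chi-square, the 2x2 layout, a final analysis that repeats the interim plan, and logistic regression attached to secondary endpoints. Nowhere is the score named as a covariate for the primary estimate.

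**2. Is the score a legitimate baseline covariate?** Data Collection dates it before discharge and General Approach at discharge. Randomisation is the next morning, so on either wording allocation cannot affect it.

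**3. The plan's own figures (Table 1).** Inputs: control rate 13.52%, two-sided alpha 0.048 (z = 1.977), power 80% or 90% (z = 0.842 or 1.282), 1117 or 1582 per arm.

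Uncorrected: n = [z_α √(2p̄(1−p̄)) + z_β √(p₁(1−p₁) + p₂(1−p₂))]² / d²

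Corrected: n_c = (n/4)[1 + √(1 + 4/(n d))]²

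Example, 13.52% vs 9.6% at 80% power: p̄ = 0.1156, d = 0.0392; n = [(1.977 × 0.4522 + 0.8416 × 0.4513)/0.0392]² ≈ 1056, and n_c ≈ 1107. Solving for the detectable intervention rate at the stated sizes:

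| Per arm, power | Table 1 | Corrected | Uncorrected |
|---|---|---|---|
| 1117, 80% | 9.6% | 9.62% | 9.70% |
| 1117, 90% | 9.1% | 9.07% | 9.15% |
| 1582, 80% | 10.2% | 10.22% | 10.28% |
| 1582, 90% | 9.7% | 9.74% | 9.80% |

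All four printed rates match the corrected test and none matches the uncorrected one. This agrees with the only version that Statistical Analysis names.

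**4. Size of the continuity question.** Exact binomial power at alpha 0.048 falls with the correction from 82.4% to 80.5% (1117 per arm, 13.52% vs 9.6%) and from 89.8% to 88.8% (1778 per arm, 13.5% vs 10%). Corrected type I error is 0.041 to 0.043. In a recalculation for 13.5% vs 10% at 90% power and alpha 0.05, the choice moves n from 1777 to 1834 per arm, a difference of 57.

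**5. Gain from adjustment.** The AUC is an assumption, 0.60 to 0.80, which corresponds to R² of about 0.015 to 0.173 on the risk scale. The simulation used 20,000 trials per cell, a logit-normal score, a standardised risk difference with robust standard error, and alpha 0.048. It compared this with the uncorrected chi-square on the same data. Gains in power points:

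| AUC | 0.60 | 0.65 | 0.70 | 0.75 | 0.80 |
|---|---|---|---|---|---|
| 1117 per arm | 0.5 | 1.2 | 2.5 | 3.7 | 6.0 |
| 1778 per arm | 0.3 | 0.9 | 1.7 | 2.9 | 4.5 |

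A separate run put the upper end at 1778 per arm at 4.6.

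Rough check, replacing n by n/(1−R²): at 1117 per arm and R² = 0.067, 1117/0.933 ≈ 1197, and power goes from 82.2% to 84.7%, a gain of 2.5 points.

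**6. Robustness, 1117 per arm, AUC 0.60, 0.70, 0.80.** With 10% of scores missing (median fill plus indicator), the gains are 0.3, 2.2 and 5.2 points. With a score not linear on the logit scale, a linear term gains 0.3, 1.7 and 5.4, and a 4-knot spline 0.4, 2.1 and 5.6. In these two settings, null rejection of the adjusted test at 0.048 was 0.047 to 0.050. At the interim level of 0.005 with 558 per arm it was 0.0050 to 0.0052. There is no inflation beyond simulation error.

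**The case against.** **The plan is valid as it stands.** A simple 2x2 intention-to-treat comparison is unbiased, is easy to explain to hospital leadership and matches the test used for sizing. The benefit of adjusting rests on an AUC that the documents do not give, and at 0.60 it is half a point or less. All of this stands. It limits the point to precision and is why the chi-square should be kept as support.

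**The score may already be in the models.** Outcome Measures counts readmission within subgroups, including by score, as a secondary outcome. The Study Summary adds interaction analysis, and General Approach examines outcomes by score in all three phases. These passages describe subgroup and interaction work. They do not give a score-adjusted overall treatment effect, so this objection does not hold, although the loose wording deserves tidying.

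**A stronger reading of the sizing.** The Study Summary gives "Sample size: 3556 (1778 per arm"), and the uncorrected formula returns 1777 for 13.5% vs 10% at alpha 0.05. A reader might infer that the Study Summary used an uncorrected test and Table 1 a corrected one. The documents do not support that. Power Calculation gives 508 eligible patients per month and the Study Summary about 7 months: 508 × 7 = 3556, and 3556/2 = 1778 exactly. The figure is thus explained as an accrual projection. The detectable rate at that size (90% power, control 13.52%, alpha 0.048) is 10.00% uncorrected and 9.95% corrected, and both print as 10%.

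**Conclusion.** The point holds as one of precision. By inference from several sections, the primary comparison is unadjusted, and a suitable pre-randomisation covariate already in the dataset is not used for it. Under an assumed AUC of 0.60 to 0.80, adjustment is worth about 0.5 to 6 power points at 1117 per arm and 0.3 to 4.6 at 1778 per arm. At AUC 0.70 it is about 2.5 and 1.7 points. It may be small, but the cost is close to nil, so the change is worth making.

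A reader might infer bias, or a trial short of its stated power. Neither follows: randomisation makes the unadjusted test valid, and Table 1's rates reproduce with the corrected chi-square. The continuity question (1 to 2 power points) is a clarification and not a demonstrated conflict. The Kruskal-Wallis wording affects descriptive and exploratory comparisons only.

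**What to change.** Before any outcome by arm is seen, amend Statistical Analysis as follows.

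1. **Primary analysis.** Intention-to-treat logistic regression of 30-day readmission on arm and the continuous pre-discharge risk score, entered as a linear term, with median fill plus a missing indicator for absent scores. Report a standardised risk difference with a robust (delta-method) confidence interval, tested at 0.005 at the interim and 0.048 at the final analysis. A risk difference stays on the scale of the plan's target differences; an adjusted odds ratio would not.
2. **Supportive analysis.** Keep the unadjusted chi-square, state whether it is continuity corrected, and use the same version in any sample-size recalculation under Appendix V, item 8. If the correction is dropped, say that this departs from the test behind Table 1.
3. **Test pairing.** Chi-square for categorical variables; Mann-Whitney for continuous variables in two groups; Kruskal-Wallis for continuous or ordinal variables across reached, not reached and control.

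The cost is SAP wording, since the score is already to be extracted. The downside is that the primary test no longer exactly matches the chi-square used for sizing, and a missing-score rule has to be stated.

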#### Outcome Measures

### Primary Outcome for this study is readmission within 30 days

Secondary Outcomes include evaluating: The primary outcome of readmission within 30 days within prespecified subgroups (age, gender, race, health literacy level, established primary care status, patient satisfaction, Medicare readmission penalty diagnosis status, readmission risk score), patient satisfaction between the study arms measured as mean Hospital Consumer Assessment of Healthcare Providers and Systems (HCAHPS) patient satisfaction scores, all cause VUMC ED visits, the need for assistance with discharge plan implementation, and mortality within 30 days.

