### **Appendix IV- Study Variable Summary**

#### Phone Call Study Patient Variates

BASELINE PATIENT DATA
First name
Last name
Zipcode
Medical record number
Established Primary Care Yes
No

Health Literacy BHLS Education level

Race Black White

Latino Non-white Hispanic

Multiple Races Unknown

Primary Language English

Spanish Arabic Other

Number of Hospitalizations in Prior Year

Complicating Baseline Comorbidities (Natural Language Processing)

Congestive heart failure

COPD

Readmission penalty dx - AMI, HF, PNA, COPD,

CABG, Total hip/knee repair, and stroke

Diabetes

Outpatient hospice Substance abuse Depression INDEX HOSPITALIZATION DATA

Intervention Arm Encounter Number Date of admission Time of admission

Admission day of the week Admission Diagnosis #1 Admission Diagnosis #2 Admission Diagnosis #X Highest bed level

Floor ICU Discharge Service Riven Morgan

> Geriatrics Palliative Care

Discharge Diagnosis #1 (ICD-10)
Discharge Diagnosis #2 (ICD-10)
Discharge Diagnosis #3 (ICD-10)
Discharge Diagnosis #4 (ICD-10)
Discharge Diagnosis #X (ICD-10)

Discharge Date Discharge Time

Discharge Location/Disposition

Readmission penalty dx cohort- AMI, HF, PNA, COPD, CABG, Total hip/knee repair, and stroke

Number of medications upon discharge

VUMC Cornelius Readmission Risk Score Patient satisfaction (Press Ganey Score, 1-5)

READMISSION HOSPITALIZATION DATA

Date of admission Time of admission Admission Diagnosis #1 Admission Diagnosis #2

Admission Diagnosis #X Highest bed level Floor

ICU
Discharge Diagnosis #1 (ICD-10)
Discharge Diagnosis #2 (ICD-10)
Discharge Diagnosis #3 (ICD-10)

Discharge Diagnosis #4 (ICD-10)

Discharge Diagnosis #X (ICD-10)

Readmission penalty dx - AMI, HF, PNA, COPD, CABG, Total hip/knee repair, and stroke

Discharge Date
Discharge Time
Discharge Location

Patient satisfaction (Press Ganey Score, 1-5)

Extra-Institutional Data

Survival Data (at 30 days)

Non-VUMC TN Readmission (at 30 days post VUMC

admit)

(minimum data = yes/no)

CALL INTERVENTION DATA

1st Contact

Time of first call Date of first call

Final Contact

Time of Final Contact Date of Final Contact

Call attempts

1 2 3

Not eligible AMA Facility Placement Deceased

Already seen in clinic CRC patient

Patient currently admitted/readmitted

Call status

Success

Unsuccessful - Wrong Number

Unsuccessful - Refused

Unsuccessful - Patient Call Back Requested

Unsuccessful - Patient Not Available

Unsuccessful - No Answer

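### The model named for the secondary endpoints, logistic regression, does not match patient satisfaction, which is defined as a between-arm comparison of mean scores

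*Combined protocol and SAP*

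**What the plan says.** Outcome Measures lists the secondary outcomes in one sentence. It opens with "The primary outcome of readmission within 30 days within prespecified subgroups", continues with "patient satisfaction between the study arms measured as mean Hospital Consumer Assessment of Healthcare Providers and Systems (HCAHPS) patient satisfaction scores", and ends with "all cause VUMC ED visits, the need for assistance with discharge plan implementation, and mortality within 30 days". Data Collection again counts satisfaction scores among the secondary outcome measures. Appendix IV records the variable as "Patient satisfaction (Press Ganey Score, 1-5").

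The Statistical Analysis section gives one multivariable rule for these outcomes: "we will examine the relationship between treatment assignment and our secondary endpoints using logistic regression". It states no cut-point, ordinal form or linear alternative.

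The General Approach bears on this in two places:
- It says "We will then examine secondary outcomes of all cause ED visits to Vanderbilt or VHAN ED and mortality". Satisfaction is not named there as an outcome and appears only among the characteristics by which outcomes will be examined.
- On need for assistance it says "we will use descriptive statistics to quantify the need for patient assistance with discharge plan implementation", and it limits this to a count "among patients in the intervention arm who are called and reached".

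Appendix V puts satisfaction among the outcomes to be compared by intention to treat, without naming a test or model.

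**The concern.** The outcome and the model describe different quantities. A mean score calls for a difference in means, whereas binary logistic regression gives an odds ratio for a yes/no event. Someone following the Statistical Analysis section literally would first have to turn the score into a yes/no variable, and the plan does not say how.

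Satisfaction is not incidental to this trial. The Objective lists it among the effects to be quantified, Study Design makes it part of the trial's question, and the Study Timeline brings it into both the interim and the final analysis. If the cut-point is left open, two competent analysts could report different effects from the same data, and the choice could be made with scores already in view. The reported result would also not be the quantity that Outcome Measures promises.

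**Working it through.** The plan gives no figure on this point, so there is none to reproduce. The check compares each secondary outcome's scale and population with the stated model.

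**Outcome by outcome**

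| Secondary outcome | Scale | Observed in | Binary logistic regression on arm |
|---|---|---|---|
| Readmission within subgroups | yes/no | both arms | fits |
| ED visits | yes/no, if taken as any or none | both arms | fits |
| 30-day mortality | yes/no | both arms | fits |
| Satisfaction | mean score; 1-5 in Appendix IV | both arms | does not estimate the stated quantity |
| Need for assistance | assistance items | reached intervention patients | not planned; descriptive analysis given |

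Satisfaction is the only outcome with a planned between-arm comparison that the named model does not match.

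**What a cut-point would do.** For a score Y from 1 to 5,

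mean(Y) = 1 + P(Y≥2) + P(Y≥3) + P(Y≥4) + P(Y≥5).

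The difference in means is therefore the sum of four differences in proportions, one for each possible cut-point. A binary logistic model uses one of the four. If a share d of patients in one arm moved from 3 to 4, that arm's mean would rise by d while the proportion scoring 5 would not change. A model of the top score would show nothing.

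A numerical check of the identity uses assumed proportions of 0.03, 0.05, 0.12, 0.30 and 0.50 for scores 1 to 5. The documents give no distribution.
- Directly: 0.03 + 0.10 + 0.36 + 1.20 + 2.50 = 4.19.
- By cut-points: 1 + 0.97 + 0.92 + 0.80 + 0.50 = 4.19.

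**What can be fitted.** Scores were simulated from those proportions, 300 per arm, with no true difference between arms:
- Binary logistic regression on the raw score stops with an error, because the outcome lies outside the unit interval.
- A proportional-odds (ordinal logistic) model fits, with a log odds ratio of 0.033 and standard error 0.153.
- A logistic model of score 5 against less than 5 also fits, with a log odds ratio of -0.053.

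The last two are small estimates from data with no effect. They show only that both models run and that they give different numbers. The plan specifies neither, and neither estimates a difference in means.

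**Does other text fill the gap?** The Mann-Whitney test named for continuous outcomes belongs to the univariate sentence, which is about differences among patient characteristic groups. Read generously, it gives a valid unadjusted test of satisfaction by arm. It does not give a mean difference or an adjusted estimate.

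**The case against.** The strongest defence is that the logistic sentence should be read with the General Approach, which shortly before names ED visits and mortality as the secondary outcomes to be examined. Both can be binary and both exist in each arm, so on that reading the sentence contains no error. This softens the point but does not remove it. Outcome Measures and Data Collection both list satisfaction as a secondary outcome, and the narrower phrase does not strike it off. If the logistic sentence does not cover satisfaction, the plan names no treatment-effect model for it at all.

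A second defence is that logistic regression can include the ordinal form. That stands, and a reader who infers that the named model cannot be fitted to satisfaction, or that it forces a dichotomy, goes too far. However, the plan does not say ordinal, and an ordinal model yields a common odds ratio, whereas Outcome Measures asks for mean scores.

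A reader might also infer a second failure: need for assistance has no control-arm values, so no treatment effect can be estimated. The algebra is right, since with one arm observed the intercept and treatment columns are identical and the design has rank 1. The documents do not support the inference, because no between-arm test of need is planned. The Objective, the General Approach and Appendix V all treat it as a description of reached intervention patients. The logistic sentence is merely worded too broadly.

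**Conclusion.** The point holds for one secondary endpoint. The plan defines satisfaction as a between-arm comparison of mean scores, and the only treatment-effect model it states is logistic regression. In binary form, that model estimates something else and needs an unstated cut-point.

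Severity is low. The primary intention-to-treat comparison of readmission, the significance levels and the sample size do not depend on it. No loss of precision can be calculated, because the documents give neither a score distribution nor a cut-point, and any percentage would rest on invented inputs. Nor do the documents show that anyone intends to choose a cut-point after seeing the data; they only leave room for it.

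The conclusion assumes that the reference to secondary endpoints includes every outcome so listed under Outcome Measures. The count of four cut-points assumes the Press Ganey 1-5 score. Outcome Measures names HCAHPS instead, and its scale is not given. A mean score on either instrument is not a yes/no outcome, so the mismatch does not depend on which is used.

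**What to change.** In Statistical Analysis, replace the logistic sentence with wording that does three things:

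1. It limits binary logistic regression on treatment assignment to ED visit (any or none) and 30-day death.
2. It analyses satisfaction undichotomised, with a linear model for the between-arm difference in mean score, robust standard errors and a 95% confidence interval. This keeps the quantity in Outcome Measures. A proportional-odds model on the 1-5 score can be named as a sensitivity analysis.
3. It excepts need for discharge-plan assistance and points to the descriptive analysis in the General Approach.

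The same edit should state whether the analysed score is HCAHPS or Press Ganey, because the ordinal sensitivity analysis as described applies to the 1-5 score. The cost is about one sentence of text. It needs no new data and no change to the sample size or to the primary analysis.
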